# 9.4 Vital signs, physical findings, and other observations related to safety

## 9.4.1 Vital Signs

Vital signs will be measured within approximately 15 minutes prior to dosing, and in addition (following implementation of Protocol Amendment 3), pulse and blood pressure only will be

measured approximately 30 minutes after dosing with study medication. Study participants should be sitting for at least 5 minutes prior to and during the collection of blood pressure and pulse rate measurements. Vital signs to be collected are pulse, systolic/diastolic blood pressure measurement, and temperature.

For pre-dose measurements, if more than one results appears for a specific visit, then the pre-dose results are averaged. The same will occur for post dose measurements. All data will be listed, including the averages. If measurements are labeled as pre-dose in the CRF, but when compared to dosing, it is actually post-dose, the analysis label will reflect a post dose measurement. The same will occur for post-dose measurements.

Descriptive statistics for observed values and change from pre-dose to post-dose pulse and blood pressure when available, will be presented for each visit for each vital sign parameter.

Vital signs summaries will be provided for the Reduced CZP Dose, Original CZP Dose, and Any CZP Dose) and by Baseline weight group.

A summary of the incidence of markedly abnormal vital signs results by post-baseline scheduled visit will be presented for temperature, blood pressure, and pulse rate parameters. Details of markedly abnormal values will be listed by study participant and parameter for which there is at least 1 markedly abnormal result recorded. Definitions of markedly abnormal values are given below in Table 9–5.

Markedly abnormal high temperature is >40.0 degrees Celsius (>104.0 degrees Fahrenheit) while a markedly abnormal low temperature is 32-35 degrees Celsius (89.6-95 degrees Fahrenheit). Vital signs data will be listed, including the flagging of markedly abnormal values.

Table 9–5: Definitions of Markedly Abnormal Vital Signs Values

Parameter	Age Range	Abnormality Criteria
Pulse Rate	3y<	<60
(beats/minute)	<12y	>130
Ċ.	12y -	< 50
7/0	<17y	≥ 120
Jedie	≥17y	<60
		>100
Systolic Blood	3y -	<80
Pressure	<12y	>140
(mmHg)	12y -	<90
	<17y	>160
	≥17y	<90
		>140
		>160
	Зу -	<50
	<12y	>80

Parameter	Age Range	Abnormality Criteria
Diastolic Blood	12y - <17y	< 50 ≥105
Pressure	≥17y	<50
(mmHg)		>90
		>100

#### 9.4.2 Other safety variables

#### 9.4.2.1 Height and weight

Descriptive statistics for Baseline and post-Baseline values at selected time points of interest, and change from Baseline for selected time points for percentile height-for-age and percentile weight –for-age (based on growth curves and percentile calculation methods published by CDC for children age 2-20 that was available on 27April 2016 at ... http://www.cdc.gov/growthcharts/clinical charts.htm ) will be summarized by Baseline age group and gender for the Reduced CZP Dose, Original CZP Dose, and Any CZP Dose. All weights and heights will also be listed.

#### 9.4.2.2 Tanner stages

Assessments of study participants' developmental stages on external genitalia and pubic hair (boys) and on breast and pubic hair (girls) will be performed to determine Tanner stages, for those who have not reached Tanner stage V. A summary of shift table of Tanner stages from baseline to relevant post-treatment visit(s) (48 week, 96 week, etc) by age and gender will be provided for the Reduced CZP Dose, Original CZP Dose, and Any CZP Dose. Overall Tanner stage at each visit is derived as the minimum stage of the 2 components. If one component is missing at a visit, then the overall stage will be set to missing for that visit.

No imputation of missing data will be implemented. Tanner stages will be listed by visit for each study participant.

## Physical examination 9.4.2.3

Physical examination findings will be recorded in the CRF only at Screening. Details of subsequent physical examinations should be recorded in the source documentation. Clinically relevant changes in subsequent physical examinations will be recorded as AEs.

Physical examination findings at Screening will be listed.

#### 9.4.2.6 **Tuberculosis assessments**

A tuberculin purified protein derivative (PPD) skin test, which is not mandatory for all study participants, will be done ≤3months before Screening, at Week 48, and then yearly thereafter. PPD tests should be read by a trained health care worker between 48 and 72 hours after injection. QuantiFERON TB GOLD testing at Screening is required to be performed by the central lab if the study participant has a documented history of severe positive PPD reaction or a documented history of BCG vaccination.

Following implementation of Protocol Amendment 3, a chest radiograph (anterior-posterior view at minimum, but preferably anterior-posterior and lateral) must be taken for study participants with a positive or repeatedly indeterminate IGRA or PPD testing or TB questionnaire indicating an increased study participant's risk of exposure or infection with TB (study participants 2 to 4 years of age with a written documentation of BCG vaccination) at Screening. If a study participant has had a recent radiograph of the chest within approximately 3 months prior to Screening, it may be used in lieu of the protocol required radiograph. All chest imaging must be read by a qualified radiologist/pulmonary physician who is specifically required to look for evidence of active TB or inactive TB.

The TB questionnaire will be completed twice at each visit, once by the study participant and once by the caregiver.

Tuberculosis testing, chest radiograph results and questionnaire results will be listed for each study participant.

## **EFFICACY ANALYSES** 10

Efficacy will be analyzed using the FAS. All efficacy results will be summarized overall and by Baseline weight group and will be provided for the Original CZP Dose, Reduced CZP Dose, and the Any CZP Dose. For subgroup efficacy analyses, summaries by Baseline age group, concomitant MTX use, and ADAb titer classification will be presented pooling across all weight groups unless otherwise specified. In addition, selected summaries will also be presented by gender and race.

In addition to the efficacy summaries described below, all efficacy results will be listed by study participant data listings.

Confidential

In Section 10, the analyses described for all efficacy variables below will be generated for the and any extensions or variations thereof. final analysis. For the Updated Week 24 Interim analysis, only efficacy data up to and including Week 24 was presented in the analyses described in Section 10 for the following variables:

- PedACR30/50/70/90
- Number of joints with active arthritis
- Number of joints with limitation of range of motion
- Physician's Global Assessment of Disease Activity
- Childhood Health Assessment Questionnaire
- Parent's Global Assessment of Overall Well-Being
- C-Reactive protein
- Juvenile Arthritis Disease Activity Score 71-joint

For the Updated Week 24 Interim analysis, all reported data for other efficacy variables were listed only; any calculations described for the final analysis were not performed. These Duration of Morning Stiffness

Parent's Assessment of Arthritis Pain

Faces Pain Scale Revised

JIA Pain

Fatig included the following variables:

- Fatigue Assessment Scale, and
- Juvenile Arthritis School Attendance and Caregiver Work Productivity Survey.

## Statistical analysis of the primary efficacy variable 10.1

The primary objective of this study is to evaluate PK and safety; therefore there is no primary efficacy variable.

## 10.3 Analysis of other efficacy variables

Continuous endpoints will be summarized using observed case, as for the Physician's Global Assessment of Disease Activity.

## 10.3.1 PedACR30, PedACR50, PedACR70, and PedACR90

The PedACR30, PedACR50, PedACR70, and PedACR90 response rates as compared to Baseline at every visit (including Week 16) except the Final Visit will be summarized. Plots of PedACR30, PedACR50, PedACR70 and PedACR90 response rates (combined on the same plot) by visit will be provided by the same CZP dose groups as in the summary tables above, overall and by Baseline weight group.

PedACR30, PedACR50, PedACR70, and PedACR90 response rates will also be summarized by Baseline age group, concomitant MTX use, ADAb titer classification, gender and race pooling across all Baseline weight groups.

Plots will be produced to show the percentage of PedACR30/50/70/90 responders by visit and ADAb titer classification.

## 10.3.2 PRINTO/PRCSG standard joint examination

The following 75 joints are to be examined for swelling, pain on motion (POM), tenderness, and limitation of motion (LOM) by the Investigator, another delegated physician, or an appropriately qualified medical professional who has had documented training on how to perform these assessments correctly. Preferably the same assessor should evaluate the study participant at each arthritis assessment, as per PRINTO/PRCSG guidelines. The individual with this delegated duty must be listed on Form 1572.

- Upper body (6) bilateral temporomandibular, sternoclavicular, and acromioclavicular joints
- Upper extremity (34) bilateral shoulders, elbows, wrists, metacarpals (MCP I, II, III, IV, and V), proximal interphalangeals (PIP I, II, III, IV, and V) and distal interphalangeals (DIP II, III, IV, and V)
- Lower extremity (30) bilateral hips, knees, ankles, subtalar, tarsi, metatarsophalangeals (MTP I, II, III, IV, and V), and proximal interphalangeals (PIP I, II, III, IV, and V)
- Spinal (5) cervical spine, thoracic spine, and lumbar spine, and bilateral sacroiliac joints Joint assessment will be based on a 2-point scale as unaffected (Grade 0) and affected (Grade 1). If a joint is not evaluable at Baseline, then that joint is set to missing throughout the study.

## 10.3.2.1 Joints with active arthritis

The number of joints with active arthritis is the number of joints with:

- Grade 1 for swelling, or
- Grade 1 for LOM with POM, or
- Grade 1 for LOM with tenderness.

The count of joints with active arthritis is based on 71 of 75 joints from the PRINTO/PRCSG standard joint examination. Although 75 joints are included in the PRINTO/PRCSG standard joint examination, bilateral sacroiliac joints are not assessed for swelling or LOM and as a result are not included in the active arthritis count. Additionally, cervical, thoracic and lumbar joints are treated as a single composite joint in the computation of the number of joints with active arthritis. If 1 or more of these 3 spinal joints satisfy the criteria for joints with active arthritis, then the composite joint will be counted as a joint with active arthritis.

The assessment for swelling is made on 66 joints from the above list. The hip, subtalar, cervical spine, thoracic spine, lumbar spine, and sacroiliac joints are excluded. Artificial and ankylosed joints are excluded from both tenderness and swelling assessments. Joints treated with an intra-articular corticosteroid are also not assessed.

Eleven joints are not assessed for both LOM and swelling, and consequently active arthritis status will be based on the available partial assessments performed for those joints. Bilateral sternoclavicular and acromioclavicular joints are not assessed for LOM and as a result the

joints with active arthritis status will be based only on swelling. Conversely, bilateral hip and subtalar joints are not assessed for swelling and as a result active arthritis status will be based only on LOM. Cervical, thoracic and lumbar spine joints are also not assessed for swelling and as a result active arthritis status will be based only on LOM.

In addition, joints with completely missing assessments that are otherwise expected to be evaluated will be treated as missing with respect to joints with active arthritis status. For example, MCP joints should be assessed for swelling, POM, tenderness and LOM at all visits. If all assessments for a given MCP joint are missing at a given visit, the joint will be treated as missing and will not be included as an assessed joint in the calculation of the active arthritis count. However, if partial data are available for a given joint, and the available data are sufficient to indicate that a given joint has active arthritis (eg, joint is assessed as swollen, but LOM and/or POM assessment is missing), the joint will be classified as a joint with active arthritis. However, if only partial data are available, and the partial data indicate that the joint is unaffected, the joint will also be treated as missing for the determination of the number of joints with active arthritis at that time point.

The active arthritis count will be weighted by the number of joints assessed:

$$AAC = \frac{71 * \sum_{i=1}^{n} JAA}{\sum_{i=1}^{n} JA}$$

where AAC=active arthritis count, JAA=number of joints with active arthritis, and JA=number of joints assessed. If more than 50% of the joints are not assessed, then the count of joints with active arthritis will be set to missing.

The number of joints with active arthritis and change from Baseline in number of joints with active arthritis will be summarized (observed case) for every visit except the Final Visit.

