### 10.3.9.2 Final Analysis

A study participant will be considered to be in CID at a given point in time if they meet all of the following criteria:

- No joints with active arthritis: based upon both (1) a "No" response to the question "Has the subject experienced any of the following since the last visit Joint(s) with active arthritis?", and 0 joints with active arthritis at the current visit
- No fever, rash, serositis, splenomegaly, or generalized lymphadenopathy attributable to JIA: based upon a "No" response to the question "Has the subject experienced any of the following since the last visit Fever, rash, serositis, splenomegaly, or generalized lymphadenopathy attributable to JIA?"
- No active uveitis as defined by the Standardization of Uveitis Nomenclature Working Group: based upon a "No" response to the question "Has the subject experienced any of the following since the last visit Active uveitis as defined by the Standardization of Uveitis Nomenclature Working Group?"
- CRP within normal limits in the laboratory where tested or, if elevated, not attributable to JIA: based upon a "No" response to the question "Has the subject experienced any of the following since the last visit Elevated CRP levels attributable to JIA?"
- Physician's Global Assessment of Disease Activity score of best possible on the scale used (ie, 0mm on the 100mm VAS): based upon VAS score at current visit

Duration of morning stiffness of ≤15 minutes: based upon duration of morning stiffness at current visit

The 6 criteria above will be used to derive CID. If any of the 6 criteria cannot be assessed due to missing data, the study participant will be assumed not to have achieved derived CID at the corresponding visit.

Derived CID will be assessed at every post-Baseline visit except the Final Visit.

The n and percentage of study participants with derived CID will be summarized for each post-Baseline visit. The exact 95% CI for the percentage will also be presented.

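### Section 10.3.2.1 contradicts itself on whether limitation of motion alone makes a hip, subtalar or spine joint active, and the choice decides derived CID and CRM for any participant with isolated limitation there

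*SAP*

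**What the plan says.** SAP Section 10.3.2.1 opens with three routes to an active joint: "Grade 1 for swelling, or" "Grade 1 for LOM with POM, or" "Grade 1 for LOM with tenderness". LOM by itself is not one of them.

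Further down, the section deals with eleven joints for which either swelling or LOM is not examined. For four of them it says that "bilateral hip and subtalar joints are not assessed for swelling and as a result active arthritis status will be based only on LOM". For the spine it says: "Cervical, thoracic and lumbar spine joints are also not assessed for swelling and as a result active arthritis status will be based only on LOM". The sternoclavicular and acromioclavicular joints get the mirror-image rule: they are judged on swelling, because LOM is not examined there.

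Another sentence in the section points the other way for the spine. The composite spinal joint is counted "If 1 or more of these 3 spinal joints satisfy the criteria for joints with active arthritis", which refers back to the general definition.

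The section also says: "Artificial and ankylosed joints are excluded from both tenderness and swelling assessments". It does not say how LOM in those joints enters the active count.

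The count is used downstream. Derived CID (Section 10.3.9.2) requires "0 joints with active arthritis at the current visit", and derived CRM (Section 10.3.10.2) requires sustained derived CID. The count is also a PedACR core measure (Section 10.2) and a JADAS-71 component (Section 10.3.8).

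**The concern.** The reason given for the special rule is that swelling is not examined in these joints. That removes the first route to being active. It gives no reason to relax the other two, both of which require POM or tenderness alongside LOM. Section 10.3.2 lists POM and tenderness among the signs examined, and Section 10.3.2.1 does not exempt hips, subtalar joints or the spine from either.

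Two competent programmers could therefore derive different active counts from the same data. Derived CID turns on whether the count is exactly zero, so one unit is enough to change a participant's status. An investigator could answer No to the CRF question about active joints and the participant would still fail the joint criterion. A wrong CRM status would carry into both Kaplan-Meier summaries. It would also reach the expected-dose rule in Section 7 and the dosing-gap deviations in Section 3.4, which depend on derived CRM.

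**Working it through.** **1. The plan's joint counts (list in Section 10.3.2).**
- All joints: 6 + 34 + 30 + 5 = 75.
- Active count: 75 − 2 sacroiliac − 2 (three spinal joints become one unit) = 71. Stated: 71.
- Swelling: 75 − 2 hip − 2 subtalar − 3 spine − 2 sacroiliac = 66. Stated: 66.
- LOM: 75 − 2 sternoclavicular − 2 acromioclavicular − 2 sacroiliac − 2 (spine composite) = 67. Stated in Section 10.3.2.2: 67.
- Partly examined joints: 2 + 2 + 2 + 2 + 3 = 11. Stated: 11.

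All the stated counts reproduce, so the problem lies in the rule and not in the joint list.

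**2. Units touched by the rule.** 2 hip + 2 subtalar + 1 spine composite = 5, and 5/71 = 7.0%.

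**3. Effect of one unit with LOM but no POM or tenderness, no other joint being active.** The plan's formula is AAC = 71 × JAA / JA, where JAA is the number of active joints and JA the number assessed.

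| Joints assessed | Literal LOM-only rule | Three-route definition |
|---|---|---|
| 71 | 71 × 1/71 = 1.00 | 0 |
| 66 | 71 × 1/66 = 1.08 | 0 |
| 50 | 71 × 1/50 = 1.42 | 0 |

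Under the literal rule the count is never below 1, so the CID joint criterion fails at that visit. Under the definition it is met.

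**4. Effect on the active-joint measure in PedACR (constructed example).** Assume 6 joints that are active under the definition and all resolve, f further units with isolated LOM that persists, and all 71 units assessed. Measured improvement is 6/(6 + f), against 6/6 = 100% under the definition.
- f = 1: 6/7 = 85.7%
- f = 2: 6/8 = 75.0%
- f = 3: 6/9 = 66.7%

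On this one measure, f = 1 or 2 misses the 90% threshold but meets 30, 50 and 70. f = 3 also misses 70.

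**5. Effect on JADAS-71.** The active count is added in directly, so with all 71 units assessed each such unit adds 1 point to the score at that visit. If the same LOM is present at Baseline and later, the change is unaffected: (6 + f) − (0 + f) = 6. The level shifts, and so does the percentage improvement in step 4.

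**The case against.** The strongest reply is that the paragraph only says which routes remain when one sign is unavailable. On that reading, judging a joint only on LOM means using the two LOM routes, both of which still need POM or tenderness. The spine-composite sentence supports this by pointing back to the general criteria. The reading is possible, and it means the plan cannot be said to have settled on LOM alone. It does not remove the defect. The paired rule for sternoclavicular and acromioclavicular joints does mean a single sign, so the one-sign reading of its counterpart is at least as natural.

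A second reply is that the general sentence in Section 10.3.2 also says all 75 joints are examined for swelling and LOM, which later text restricts. It therefore does not prove that POM and tenderness are recorded for these particular joints. That stands, and the fix should confirm it.

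Third, the endpoints affected are not primary. Section 10.1 names no primary efficacy variable, Section 3.1 plans no hypothesis testing, and CID, CRM and JADAS-71 are among the other variables. PedACR needs improvement in only 3 of 6 core measures, so step 4 does not by itself decide a response. This limits the consequence but leaves the contradiction in place.

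A reader might go further and infer that fixed joint damage permanently blocks remission, or that an ankylosed or replaced hip is scored active for the rest of the study. The documents do not support either. The plan treats LOM as able to improve: it is a PedACR core measure and is summarized as change from Baseline. Section 10.3.2 sets a joint that is not evaluable at Baseline to missing throughout. The plan is silent on LOM in artificial and ankylosed joints, which is a gap to close and not a stated rule.

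**Conclusion.** The point holds as an internal contradiction in Section 10.3.2.1 that changes endpoint values according to how it is programmed. It concerns 5 of 71 counted units. Under the literal reading, isolated LOM in one of them moves the active count from 0 to at least 1. That alone fails derived CID, and hence derived CRM, at each visit where the LOM persists and the joint is assessed. The active joint count in PedACR and JADAS-71 is raised as well.

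This rests on two assumptions: that the sentences are programmed as written, and that some participants have LOM in these joints without POM or tenderness. The plan gives no frequency for the second, so the number of participants affected cannot be computed. The case does not depend on any claim that painless LOM is irreversible.

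**What to change.** In both sentences of Section 10.3.2.1 (hip/subtalar and spine), state that active status is *based only on the LOM criteria (LOM with POM, or LOM with tenderness)*. Add that artificial and ankylosed joints are not assessed for the active-arthritis count and so leave both numerator and denominator. Then check the joint-count program against this wording, and confirm that POM and tenderness are recorded for these joints. If LOM alone was intended, the definition at the head of the section must be amended and justified instead.

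The cost is a few lines of text and a program check, with one small downside. The Updated Week 24 Interim Analysis summarized the active joint count, PedACR and JADAS-71 and supported a regulatory re-submission (Sections 4.3 and 10). If LOM alone was programmed then, the final results for those variables may differ from what was reported, and the change must be disclosed in the CSR. CID and CRM were only listed at that interim, so clarifying now comes before their planned final-analysis summaries.

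### A partly recorded joint is set to missing even when its recorded items already rule out active arthritis, which inflates the rescaled active-joint count

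*SAP*

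**What the plan says.** SAP section 10.3.2.1 gives three alternative criteria for an active joint: "Grade 1 for swelling, or" "Grade 1 for LOM with POM, or" "Grade 1 for LOM with tenderness". Section 10.3.2 grades each item 0 (unaffected) or 1 (affected). For an ordinary joint all four items are expected; the section's example is that "MCP joints should be assessed for swelling, POM, tenderness and LOM at all visits".

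For partly recorded joints there are two rules. If the recorded items suffice to show active arthritis, the joint is classified as active. However, "if only partial data are available, and the partial data indicate that the joint is unaffected, the joint will also be treated as missing". A joint treated as missing is not counted as assessed. "The active arthritis count will be weighted by the number of joints assessed", as AAC = 71 × JAA / JA, where JAA is the number of active joints and JA the number assessed. If more than half the joints are not assessed, the count is missing.

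The only carve-out is for eleven joints that by design are not assessed for both swelling and LOM. Their status rests on the items that are assessed.

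**The concern.** The two rules treat equally decisive information differently. Recorded items that prove a joint active keep it in both numerator and denominator. Recorded items that prove a joint inactive are discarded, and the joint leaves the denominator. The rescaling then spreads the active joints over the discarded ones, as if they were active at the same rate as the rest, although the data say they are not.

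The count is one of the six PedACR core measures (section 10.2), and PedACR response at Week 16 is the secondary efficacy variable (section 2.2.2). The weighted count is also a component of JADAS-71 (section 10.3.8), and it is summarised in its own right with change from Baseline. All of these would depend partly on how completely normal joints were recorded.

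**Working it through.** **Reproducing the joint total.** The regions in section 10.3.2 give 6 + 34 + 30 + 5 = 75. Removing 2 sacroiliac joints and merging 3 spinal joints into 1 gives 75 - 2 - 2 = 71, which agrees with the statement that "The count of joints with active arthritis is based on 71 of 75 joints from the PRINTO/PRCSG standard joint examination".

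**Which patterns are decided.** Write S, L, P, T for swelling, LOM, POM and tenderness, each 0 or 1. A joint is active if S = 1, or L = P = 1, or L = T = 1. Two sets of recorded values rule this out whatever else is missing:
- S = 0 and L = 0;
- S = 0, P = 0 and T = 0.

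There are 4 × 8 = 32 patterns with exactly one item missing. Of these, 17 prove the joint active, 5 prove it inactive and 10 leave it undetermined. The five inactive ones are:
- S = L = 0 with P missing (T = 0 or 1);
- S = L = 0 with T missing (P = 0 or 1);
- S = P = T = 0 with L missing.

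With two items missing there is one more: S = L = 0 with both P and T missing.

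**How many of these the rule reaches.** This depends on the word unaffected.

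| Reading | Proven-inactive patterns set to missing | Of these, one item missing |
|---|---|---|
| Narrow: every recorded item is 0 | 4 | 3 |
| Broad: recorded items do not show activity | 6 | 5 |

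The two extra patterns on the broad reading have S = L = 0 with P = 1 or T = 1. The problem exists on either reading.

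**Size.** Suppose k proven-inactive joints are dropped, nothing else is missing and at least one joint is active. Then AAC = 71 × JAA / (71 - k), and the inflation factor is 71/(71 - k):
- k = 1: 71/70 = 1.014;
- k = 3: 71/68 = 1.04.

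If no joint is active, 71 × 0 / JA = 0 and there is no inflation.

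**Effect at a post-Baseline visit.** Take 10 active joints at Baseline and 7 at the visit, a true improvement of (10 - 7)/10 = 30.0%.
- k = 1 at the visit: 71 × 7/70 = 7.10, improvement 29.0%.
- k = 3 at the visit: 71 × 7/68 = 7.31, improvement 26.9%.

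In both cases this core measure misses the 30% level. The JADAS-71 joint component rises by 0.10 and 0.31 points respectively.

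**Effect at Baseline.** Take 10 active joints at Baseline and 8 at the visit, a true improvement of 20.0%, with 10 inactive joints dropped at Baseline.
- Dropped at Baseline only: 71 × 10/61 = 11.64 falling to 8, or (11.64 - 8)/11.64 = 31.3%.
- The same joints also dropped at the visit: 11.64 falling to 71 × 8/61 = 9.31, or 20.0%, provided none of those joints is active at the visit.

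Which case applies depends on section 10.3.2, which sets a joint that is not evaluable at Baseline to missing for the whole study. It does not say whether a partly recorded joint counts as not evaluable.

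**The case against.** The rule is explicit and programmable, and for many patterns it is right. If swelling is the missing item and the rest are 0, the joint may truly be swollen, so setting it to missing is reasonable. This stands, and the fix preserves it.

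It also rules out a stronger reading: that missing items remove only inactive joints, so the count is always too high. Ten of the 32 one-item-missing patterns are undetermined, and some of the joints removed may be active. Only the removal of proven-inactive joints pushes the count one way.

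A reader might also infer that an inflated visit count turns responders into non-responders. Section 10.2 requires improvement in at least three of six core measures, so losing this one changes the response only when exactly three had improved. The 30% example sits on the threshold by construction.

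Nor can Baseline inflation be said flatly to create spurious improvement. If the joint is then missing throughout under section 10.3.2, the factor cancels from the percentage change, as shown in the working.

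Finally, the stakes are limited. Section 10.1 states that there is no primary efficacy variable, and section 3.1 that there is no formal hypothesis testing. All of this bears on the size of the problem. None of it gives a reason to discard recorded items that already settle a joint's status.

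**Conclusion.** The point holds in a limited form. The rule discards joints that the SAP's own definition has already shown to be inactive, while keeping partly recorded joints shown to be active. The resulting inflation is 71/(71 - k), assuming at least one active joint and no other missing joints. One to three such joints give about 1.4% to 4%.

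Large factors are arithmetically possible. The 50% cut-off allows up to 35 dropped joints, a factor of 71/36 = 1.97. Nothing in the SAP suggests missing items on that scale; it gives no frequency at all, so the practical effect may be small.

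Post-Baseline inflation understates improvement in this core measure and raises JADAS-71. Baseline inflation overstates improvement only if the joint is not also set to missing throughout. The requirement of zero active joints for clinically inactive disease is not affected by the rescaling, because zero rescales to zero. The change is worth making because it uses data already collected.

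**What to change.** Replace the last partial-data sentence in SAP section 10.3.2.1 with wording such as:

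> If partial data are available, the joint is classified as not active and counted in JA when no value of the missing item(s) among those scheduled for that joint could make it active. For joints assessed on all four items, this means swelling = 0 and LOM = 0, or swelling = 0 with POM = 0 and tenderness = 0. For joints not assessed by design for swelling or for LOM, the same test is applied to the items that define their status. The joint is set to missing only when a missing item could change its status.

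This also settles patterns that the current text leaves open, such as swelling = 0, LOM = 1, tenderness = 0 with POM missing, which would be set to missing.

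The cost is this rewording and a small programming change, with no new data. Active-joint counts, PedACR and JADAS-71 were already reported in the Updated Week 24 Interim Analysis (section 10), so the CSR should note any difference from those results.
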